4.0 TREATMENT PLAN

4.1 Overview

In Phase 1, patients will be treated with a dose escalation plan for veliparib based on a 3+3 study design. The initial patient cohort will be treated with veliparib 300 mg PO twice daily and nivolumab as follows (1 cycle = 28 days):

Cycle 1-4: 240 mg IV every 2 weeks and

Cycle 5+: 480mg IV every 4 weeks

See section 4.2 for treatment administration and dosing modifications based on the planned 3+3 study design. Total cycle length is 28 days (4 weeks). Combination treatment will continue until progression of disease or intolerability with scans occurring every 8 weeks (see section 4.7.1 for possible treatment beyond progression). Patients in the expansion cohort (Phase1B) will be treated with the MTD, that is now established. This same treatment plan will be used for patients in both the dose escalation and dose expansion cohorts.

Patients will undergo a fresh tissue biopsy prior to study enrollment, unless deemed to be clinically inappropriate per PI, to evaluate pharmacodynamic changes in immune-related biomarkers. Correlatives will be assessed as detailed in section 9.0.

[Please note: . According to the modified plan for the current trial, the study will be closed after the 6 additional patients in the expansion cohort will have been recruited.]

4.2 Treatment Administration

Table 4.1: Dosing of Nivolumab and Veliparib

Drug	Dose	Route	Schedule
Nivolumab (Opdivo)	C1-4: 240mg C5+: 480mg	IV	Cycle 1-4: every 14 days Cycle 5+: every 28 days until progression of disease, intolerable toxicity, or withdrawal of consent
Veliparib	Phase I: Starting dose 300mg (see 4.3 for escalation) Phase Ib: MTD	PO	Twice a day about 12 hours apart starting 7 days before C1D1 (Induction monotherapy) continuing until progression of disease, intolerable toxicity, or withdrawal of consent

4.2.1 Veliparib

Veliparib is administered orally twice a day starting on Day 1 of each cycle. Subjects will self-administer the morning and evening doses of veliparib approximately 12 hours apart in the same calendar day. Each dose of veliparib will be taken with a glass of water and consumed over as short a time as possible (i.e., not slower than 1 capsule every 2 minutes) with or without food. During veliparib treatment, standard antiemetic therapy may be administered as appropriate, including a combination of standard antiemetic's (i.e., 5-HT3 receptor antagonists, steroids, and prochlorperazine, and/or promethazine).

It is recommended that if a subject misses a scheduled dose of veliparib and less than 6 hours have passed since the scheduled dosing time, the dose should be immediately taken. It is recommended that if more than 6 hours have passed since the scheduled dosing time, the subject should not take the missed dose but should wait and take the next regularly scheduled dose.

If the subject vomits within 15 minutes of taking veliparib, another dose will be administered. The dose may only be repeated once. If more than 15 minutes has passed from the time of oral dosing then no additional doses will be taken.

Patients will maintain a drug diary for dosing compliance each cycle. Completed drug diaries will be returned at the beginning of each cycle along with any leftover veliparib tablets and drug bottles.

See section 4.3 for details on dose escalation during Phase I and section 4.4 for toxicity management

4.2.2. Nivolumab

During Cycle 1-4, nivolumab will be administered at a fixed dose of 240 mg intravenously over approximately 30 minutes (-5 / +15 minutes) every 2 weeks (Day 1 and 15 of each cycle). Starting with Cycle 5, nivolumab will be administered at 480mg IV over 30 minutes (-10 / +15 minutes) every 4 weeks (Day 1 of each cycle). There is no premedication required for infusion. Veliparib oral doses can be taken independently of the nivolumab administration schedule.

4.2.2.1 Treatment Monitoring

Subjects will be monitored before, during, and after the 30- or 60-minute infusion of nivolumab with vital signs as follows:

Table 4.2: Time Points for Vital Signs

Before Infusion	
Pre-dose	Vitals up to 30 minutes prior
During Infusion	
Every 15 minutes	Vitals ± 5 minutes
After infusion	
Immediately following	Vitals within 5 minutes after
30 minutes post	Vitals ± 5 minutes
60 minutes post (1 st & 2 nd doses)	Vitals ± 5 minutes
3 hour observation (1 st dose only)	Observation only

In the event of a Grade ≤ 2 infusion-related reaction, the infusion rate of nivolumab may be decreased by 50% or interrupted until resolution of the event (up to 4 hours) and re-initiated at 50% of the initial rate until completion of the infusion. In subjects experiencing Grade ≤ 2 infusion-related reaction, subsequent infusions may be administered at 50% of the initial rate. Acetaminophen and/or an antihistamine (eg, diphenhydramine) may be administered at the discretion of the investigator. If the infusion-related reaction is severe or prolonged, methylprednisolone 125 mg (or the equivalent) should be administered as well. Investigators may administer steroids at their discretion as clinically indicated and per their institution’s guidelines.

Appropriate drugs and medical equipment to treat acute anaphylactic reactions must be immediately available, and study personnel must be trained to recognize and treat anaphylaxis.

4.3 Dose Escalation

Table 4.3: Dose levels based on 3 + 3 design for veliparib and nivolumab

Dose Level	Veliparib	Nivolumab
-------------------	------------------	------------------

-1	200 mg PO twice daily	C1-4: 240 mg IV every 2 weeks C5+: 480mg IV every 4 weeks
1	300 mg PO twice daily	C1-4: 240 mg IV every 2 weeks C5+: 480mg IV every 4 weeks
2	400 mg PO twice daily	C1-4: 240 mg IV every 2 weeks C5+: 480mg IV every 4 weeks

The above dose escalation plan is based on a 3 + 3 design with the starting dose of veliparib as 300 mg PO twice daily and nivolumab as 240mg IV every 2 weeks. Each cycle will be 28 days (4 weeks) in length.

4.3.1 Definition of DLT (Dose limiting toxicity)

Toxicity will be assessed using the National Cancer Institute (NCI) Common Toxicity Criteria for Adverse Events (CTCAE), version 4.03 unless otherwise specified. A DLT is defined as an AE or abnormal laboratory value assessed as at least possibly related to the study medication, occurs ≤ 28 days following the first dose of veliparib and nivolumab and meets any of the criteria listed below. Whenever a patient experiences toxicity that fulfills the criteria for a DLT, treatment with the study drug combination will be interrupted until resolution to ≤ Grade 1 or baseline, and the toxicity will be followed up until resolution. All adverse events specified below will be DLT's except those that are clearly and incontrovertibly due to extraneous causes.

The following events will be considered DLT's:

1. Grade ≥ 3 non-hematologic toxicities that represent at least a 2-grade increase from baseline with the following exceptions:
 - a. Nausea, vomiting, and diarrhea lasting ≤48 hours
 - b. Electrolyte abnormalities resolving within ≤24 hours
 - c. Hypersensitivity reactions
 - d. Alopecia
2. Grade 4 thrombocytopenia (platelets < 25.0 x 10⁹/L)
3. Grade 3 thrombocytopenia with bleeding (platelets <50.0 x 10⁹/L)
4. Grade 4 neutropenia (ANC < 0.5 x 10⁹/L)
5. Grade 3 febrile neutropenia with fever lasting for > 7 days
6. Grade 4 febrile neutropenia of any duration
7. Dosing delay due to toxicity for > 14 consecutive days from the date nivolumab or veliparib is due.

4.3.2 Dose Escalation 3+3 Rule

Table 4.4: Dose escalation plan based on 3 + 3 design for veliparib and nivolumab

Number of Subjects with DLT in the First Cycle	Escalation Decision Rule
0 out of 3	Enter 3 subjects at the next dose level.
1 out of 3	Add 3 more subjects at current dose level. • If < 2 of 6 subjects (or < 33% of subjects) experience DLT, dose escalation will proceed to the next dose level. • If ≥ 2 of total 6 subjects (or ≥ 33% of subjects) experience DLTs, then dose escalation will be stopped.*
≥ 2 out of 3 or 6	Dose escalation will be stopped.*

*For dose level 1, additional subjects will be enrolled at the previous lower dose level (-1) as needed to establish MTD with 6 patients.

*If dose escalation is stopped at dose level 2, dose level 1 will be established as the MTD if it enrolled 6 patients (<2 of 6 patients had DLT). If dose level 1 enrolled only 3 patients (0 of 3 had DLT's), 3 more patients will be added to dose level 1 to establish the MTD. From there, dose level -1 will be utilized in the case that ≥ 2 patients have DLT.

NOTE: Whichever dose level is declared the MTD must have 6 total patients treated at that level. For example, if 3 patients are treated at level 2 and 0 patients experience DLT, escalation would then proceed to level 3. However, if ≥ 2 patients at level 3 experience DLT, enrollment to level 2 would need to be re-opened to enroll an additional 3 patients at that level (with 0 or 1 DLT observed in 6 total patients) in order to declare level 2 the MTD.

4.3.3 Dose **expansion**:

The initial study design was to accrue a total of up to 50 patients (for 48 evaluable) to the study in two phases: dose escalation and dose expansion. The original design anticipated a total of 6-18 patients with advanced solid tumors or lymphoma in the dose escalation phase. 9 patients were enrolled, including 6 that were treated at the MTD of 400 mg BID.

However, due to funding issues, the study will adopt a modified plan for the expansion cohort, and will perform an early analysis of preliminary efficacy after the next 6 patients are enrolled in the expansion cohort.

This **modified plan for expansion cohort**, will accrue 6 new patients with genetic alteration for early preliminary efficacy assessment, which together with 4 previously treated patients with genetic mutation will provide total of $6+4=10$ patients, with genetic mutation. ORR will be computed at the first imaging (8 weeks). Preliminary efficacy will be evaluated by RECISTv 1.1. As exploratory analysis, irRECIST will be used to obtain preliminary efficacy as well. All ORR will use the first imaging time point whether RECIST or irRECIST.

Patients in this cohort will be treated at the MTD and the same treatment schedule will be followed as was done in the escalation phase.

The study will be considered a success if the lower 90% exact confidence bound will be $> 10\%$, i.e. if three or more successes out of $n=10$ are observed.

According to the modified plan for the current trial, the study will be closed after the 6 additional patients will have been recruited.

4.4 **Toxicity Management & Dose Delays/Modifications**

Each patient will be assessed for the development of toxicity according to the timeframe referenced in Table 5. Toxicity will be assessed according to the NCI CTCAE V4.03.

Veliparib doses may be reduced or delayed up to 28 days according to Table 4.3 and the toxicity management guidelines in Table 4.5. Missed doses will be skipped with each cycle continuing as originally planned.

Nivolumab doses cannot be modified but can be delayed or discontinued according to Table 4.6. Missed doses will be skipped, resuming at the next scheduled treatment visit.

Since the mechanism of action of nivolumab leads to T-cell activation and proliferation, immune related adverse events (irAE) may be observed, and be similar to that of other PD-1/PD-L1 checkpoint inhibitors, and may include immune-mediated pneumonitis, enterocolitis, dermatitis, hepatitis, and endocrinopathies.

Subjects should be monitored for signs and symptoms of irAEs. In the absence of an alternate etiology (i.e. infection or PD), an immune-mediated etiology should be considered for signs or symptoms of pneumonitis, enterocolitis, dermatitis, hepatitis, and endocrinopathy. In addition to the dose modifications shown in Tables 4.4 and 4.5, it is recommended that management of irAEs follow the guidelines outlined for other immune checkpoint inhibitors. These guidelines recommend the following:

- Subjects should be evaluated to identify any alternative etiology
- In the absence of clear alternative etiology, all events of an inflammatory nature should be considered to be immune-related
- Topical or inhaled steroid therapy should be considered for low-grade events
- Systemic corticosteroids should be considered for a persistent low-grade event or for a severe event
- More potent immunosuppressives (i.e. infliximab, mycophenolate mofetil, etc.) should be considered for events not responding to systemic steroids

If the investigator has any question in regards to an AE being an irAE, the investigator should immediately contact the principal investigator. Treatment modifications will not be required for AEs that are clearly not attributed to investigational drugs (such as an accident) or for laboratory abnormalities that are not deemed to be clinically significant.

Nausea and vomiting have been commonly observed in clinical trials with veliparib. Gastrointestinal toxicities, predominantly nausea and vomiting, were observed with veliparib as single-agent therapy and most frequently reported at higher doses (300 – 400 mg BID). Of the subjects treated with single agent veliparib at 300 – 400 mg BID dose levels, 15% required dose reduction, 5% delayed or interrupted dosing and 2% discontinued due to nausea. To optimize dose intensity and maintain subject quality of life, early initiation or prophylactic management with scheduled anti-emetic therapy (5HT-3 antagonists, metoclopramide, prochlorperazine) and/or lorazepam should be considered. In addition, it has also been observed that tolerance to these toxicities may develop over time. Management should include counseling regarding these toxicities and may include interruption of dosing, dose modification or veliparib discontinuation.

Treatment modifications may be required in the event of treatment-related toxicity. General guidelines regarding treatment modification are provided in Table 4.5 and 4.6. **Dose modifications should be implemented only if toxicities are attributed to respective drugs (nivolumab or veliparib). If there is uncertainty or overlapping toxicities, both drugs should be held and or dose modified according to the guidelines.**

All toxicities will be graded according to NCI CTCAE V4.03 (Appendix B).

Should a female patient become pregnant or suspect she is pregnant while participating in this study, she should inform her treating physician immediately. Similarly if a male patient impregnates a female, the treating physician should be informed.

4.5 Dose Reductions

4.5.1 Veliparib

The following are guidelines for dose reductions, delays and discontinuation of veliparib monotherapy.

Subjects should have an ANC $\geq 1,500/\text{mm}^3$ and a platelet count $\geq 100,000/\text{mm}^3$ prior to each cycle.

For any subject who experiences Grade 3 or 4 toxicity despite optimal supportive care (with the exception of anemia, alopecia, and non-treatment related clinically insignificant laboratory abnormalities), and the toxicity is not attributable to underlying disease, the veliparib dose will be held until the toxicity resolves to Grade 1 or lower or to baseline if Grade 2 is present at the time of study entry. Interruptions of veliparib for events that are clearly not related to therapy (e.g., underlying cancer, planned surgical procedures, or acute viral illnesses), do not necessitate a dose reduction.

The dose of veliparib will be managed according to Table 4.5 below, and the dose levels in Table 4.3:

Table 4.5: Veliparib related toxicity management guidelines

Toxicity	Grade	Dose Adjustment and Management Recommendations
Hematologic Toxicities		
Anemia	1 $\geq 10.0 - \text{LLN g/dL}$	No dose adjustment required.
	2 $\geq 8.0 - < 10.0 \text{ g/dL}$	No dose adjustment required
	3 $< 8.0 \text{ g/dL}$	Dose interruption for up to 28 days until recovery to grade ≤ 2 Re-initiate veliparib at the same dose.
	4 Life threatening consequences; urgent intervention indicated	Discontinue veliparib.
Thrombocytopenia	1 $\geq 75 \times 10^9/\text{L}$	No dose adjustment required
	2 $\geq 50 \times 10^9/\text{L} - < 75 \times 10^9/\text{L}$	Dose interruption for up to 28 days until recovery to ≤ 1 . Re-initiate veliparib at the same dose level. If toxicity recurs at grade 2: temporary dose interruption until recovery to grade ≤ 1 and reduce veliparib to the next lower dose level.
	3 $\geq 25 \times 10^9/\text{L} - < 50 \times 10^9/\text{L}$	Dose interruption for up to 28 days until recovery to Grade ≤ 1 . Re-initiate veliparib at the next lower dose level. If toxicity recurs at Grade 3: temporary dose interruption until recovery to Grade ≤ 1 and reduce veliparib to the next lower dose level.
	4 $< 25 \times 10^9/\text{L}$	Dose interruption for up to 28 days until recovery to grade ≤ 1 . Re-initiate veliparib at the next lower dose level. If toxicity recurs at grade 4: discontinue veliparib.

Toxicity	Grade	Dose Adjustment and Management Recommendations
Absolute Neutrophil Count	1 ≥1.5 x 10 ⁹ /L	No dose adjustment required
	2 ≥1.0 - <1.5 x 10 ⁹ /L	No dose adjustment required
	3 ≥0.5 - <1.0 x 10 ⁹ /L	Dose interruption for up to 28 days until recovery to ≥1.0 x 10 ⁹ /L. Re-initiate veliparib at the same dose level. If toxicity recurs at Grade 3: temporary dose interruption until recovery to > 1.0 x 10 ⁹ /L and reduce veliparib to the next lower dose level.
	4 <0.5 x 10 ⁹ /L	Dose interruption for up to 28 days until recovery to ≥1.0 x 10 ⁹ /L. Re-initiate veliparib at the same dose level. If toxicity recurs at Grade 4: temporary dose interruption until recovery to > 1.0 x 10 ⁹ /L and reduce veliparib to the next lower dose level.
Lymphopenia	1 ≥800/mm ³	No dose adjustment required
	2 ≥500 - <800/mm ³	No dose adjustment required
	3 ≥200 - <500/mm ³	Dose interruption for up to 28 days until recovery to Grade ≤ 1. Re-initiate veliparib at the next lower dose level. If toxicity recurs at Grade 3: temporary dose interruption until recovery to Grade ≤ 1 and reduce veliparib to the next lower dose level.
	4 <200/mm ³	Dose interruption for up to 28 days until recovery to grade ≤ 1. Re-initiate veliparib at the next lower dose level. If toxicity recurs at grade 4: discontinue veliparib.
Non-Hematologic Toxicities		
Myelodysplastic syndrome/Acute Myeloid Leukemia		Discontinue veliparib
Pneumonitis		Discontinue veliparib
Embryo-Fetal Toxicity		If patient becomes pregnant, discuss with the patient the potential hazard to the fetus.
Nausea	
5-HT3 antagonists (ondansetron, granisetron, palonosetron), dopamine antagonists (prochlorperazine, metoclopramide) and lorazepam were most frequently used to manage veliparib-associated nausea. Anti-emetics should be initially prescribed on a specified schedule (e.g., no PRN). Multiple concomitant anti-emetic medications may be needed in some cases for effective nausea management. Example regimens and combinations to consider include:
 
 ○ Ondansetron 4 or 8 mg BID ○ Lorazepam 0.5 mg Q8H ○ Ondansetron 8 MG Q8H; prochlorperazine 10 MG Q6H ○ Lorazepam 1 mg Q8H; prochlorperazine 10 mg Q6H; ondansetron 8 mg Q8H ○ Lorazepam 1 mg Q8H; ondansetron 8 mg Q8H; omeprazole 20 mg QD 	

Toxicity	Grade	Dose Adjustment and Management Recommendations
		
In addition to the use of anti-emetic medications, investigators should rely on standard clinical practice and local/country guidelines for nausea management. Patients should be proactively counseled about adherence to the prescribed supportive care.
 
Dose Interruptions Nausea related to veliparib can be managed with dose interruptions, if it is not responsive to anti-emetic therapy. Due to the half-life of veliparib of approximately 4 – 6 hours, symptom improvement/resolution typically occurs within 1 to 3 days of treatment interruption. If no improvement of symptoms is observed within this time frame, relationship of the event to veliparib should be re-evaluated.
 
Dose Reductions Subjects experiencing nausea at the initial dose level that cannot be controlled with anti-emetics should be dose reduced. If the subject was receiving anti-emetics at the initial veliparib dose level, it is also recommended that the same anti-emetic regimen be continued at the reduced veliparib dose level until symptom resolution or significant improvement. Dose reductions to below 200 mg BID are not expected to be necessary. If nausea does not improve sufficiently at the reduced dose, further dose reduction to the next lower dose level is recommended. Interruption of veliparib dosing may be attempted to determine if nausea is indeed related to veliparib.

All non-hematologic AE's attributable to veliparib in the combination treatment cycles	Grade	Dose Adjustment and Management Recommendations
	1	No dose adjustment required. Initiate appropriate medical therapy and monitor.
	2	-Dose interruption for up to 28 days until recovery to ≤ Grade 1. Initiate appropriate medical therapy and monitor. -Re-initiate veliparib at the same dose -If the same toxicity recurs at Grade 2, interrupt until recovery to ≤ Grade 1. Re-initiate veliparib at the next lower dose level.
	3	-Dose interruption for up to 28 days until recovery to ≤ Grade 1. Initiate appropriate medical therapy and monitor. -Re-initiate veliparib at the same dose -If the same toxicity recurs at Grade 2, interrupt until recovery to ≤ Grade 1. Re-initiate veliparib at the next lower dose level. -If toxicity recurs at Grade 3, discontinue veliparib.
	4	Discontinue veliparib and treat with appropriate medical therapy

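### Section 4.5.1 and Table 4.5 contradict each other on when veliparib restarts after Grade 3–4 neutropenia, and after Grade 3–4 lymphopenia in patients who entered at Grade 2

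*Combined protocol and SAP*

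**What the plan says.** Section 4.5.1 opens with a pre-cycle condition: "Subjects should have an ANC" of at least 1,500/mm³ and a platelet count of at least 100,000/mm³ "prior to each cycle". It does not say what happens if the counts are lower.

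A hold rule follows, with this scope: "For any subject who experiences Grade 3 or 4 toxicity despite optimal supportive care (with the exception of anemia, alopecia" and clinically insignificant laboratory abnormalities not related to treatment). For such a patient "the veliparib dose will be held until the toxicity resolves to Grade 1 or lower or to baseline if Grade 2 is present" at study entry. The section then sends the reader to Table 4.5 for managing the dose.

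In Table 4.5, Grade 2 neutropenia is "≥1.0 - <1.5 x 10 ⁹ /L" and calls for no change of dose. For a first Grade 3 or Grade 4 neutropenia the instruction is "Dose interruption for up to 28 days until recovery to ≥1.0 x 10 ⁹ /L. Re-initiate veliparib at the same dose level". For a recurrence it is "temporary dose interruption until recovery to > 1.0 x 10 ⁹ /L", with a dose reduction. The Grade 3 and Grade 4 lymphopenia rows require recovery to Grade 1 or lower and do not mention baseline. Platelets of 75 x 10⁹/L or more are Grade 1 and call for no change of dose.

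Section 4.3.1 adds a third rule. After a DLT, both drugs are interrupted until Grade 1 or lower, or baseline. Grade 4 neutropenia is a listed DLT.

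**The concern.** Veliparib is taken twice daily without a break, so each blood count on a visit day leads to a decision to dose or hold. Footnote n of the study timeline (section 5) has laboratory values checked against the whole of sections 4.4 and 4.5, which includes both the paragraph and the table. Where the two disagree, site staff cannot follow one without departing from the other, and two patients with the same count and history may be managed differently. At stake are patient safety and consistent dosing in a small cohort.

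**Working it through.** No sample size or error rate is involved. The check is to put the thresholds in common units, use Table 4.5's own grades, and compare the action under each text.

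**Units.** 1,500/mm³ = 1.5 x 10⁹/L, and 100,000/mm³ = 100 x 10⁹/L.

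**Entry conditions (section 3.1.9).** ANC at least 1.5 x 10⁹/L and platelets at least 100 x 10⁹/L. No minimum is set for lymphocytes.

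| Situation | Section 4.5.1 paragraph | Table 4.5 | Result |
|---|---|---|---|
| ANC 1.0 to <1.5 after Grade 3–4 neutropenia | Keep holding (not yet Grade 1) | Restart | Contradiction |
| Lymphocytes back to a Grade 2 baseline after Grade 3–4 lymphopenia | Restart | Keep holding (Grade 1 needed) | Contradiction, in this subgroup only |
| ANC 1.0 to <1.5 on Day 1, no prior Grade 3–4 event | Pre-cycle count not met, no action stated | No change of dose | Unclear |
| Platelets 75 to <100 on Day 1 | Pre-cycle count not met, no action stated | No change of dose | Unclear |
| Platelets after Grade 3–4 thrombocytopenia | Grade 1 or lower | Grade 1 or lower | Agree on grade |
| Anemia | Excepted from the hold rule | Own rows | No conflict |

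**Neutrophils.** Take an ANC of 1.2 after a Grade 3 event. The paragraph holds, because 1.2 is Grade 2. The table restarts, because 1.2 exceeds 1.0. The paragraph's baseline exception needs Grade 2 at entry, but entry requires at least 1.5, so it does not apply. If the event was Grade 4 and counted as a DLT, section 4.3.1 also says interrupt until Grade 1 or baseline, so the table then disagrees with two texts. The table also differs from itself at exactly 1.0, which is enough after a first event but not after a recurrence.

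**Lymphocytes.** Take a patient who enters at 600/mm³ (Grade 2 is 500 to <800), falls to 400 (Grade 3 is 200 to <500) and returns to 600. The paragraph allows restart at baseline. The table asks for 800 or more, a level this patient did not have at entry, within an interruption of up to 28 days. For patients who entered at Grade 1 or better, the two texts agree.

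**Start of cycle.** Take platelets of 85 x 10⁹/L on Day 1. The pre-cycle condition is not met, while the table asks for no change. Section 4.4 says missed veliparib doses are skipped and cycles continue as planned, so failing the check does not move the cycle either. Whether this patient takes veliparib that day is not stated.

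**The case against.** The best defence is that Table 4.5 governs. Section 4.5.1 says the dose is managed by it, section 4.4 points to it for reductions and delays, and a specific row is naturally read over a general paragraph. That reading is reasonable, but the protocol does not state it. The hold sentence just above the table is mandatory in form, names its exceptions, and does not list neutropenia among them. The conflict with section 4.3.1 for a Grade 4 DLT would also remain.

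For lymphopenia, the baseline clause could be read as supplementing a row that is silent on baseline. That is possible, but it needs the paragraph to qualify the table, whereas the neutrophil defence needs the table to override the paragraph. The text supports neither order expressly.

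On the pre-cycle counts the objection largely stands. The sentence says *should*, never says hold, and can coexist with a rule for in-cycle adjustment. What remains is an undefined action, not a contradiction.

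Section 4.5.1 describes its guidelines as being for monotherapy, which might seem to confine the paragraph to induction. But that description introduces the table too, and monotherapy lasts only 7 days, so a condition that applies before every cycle cannot be limited to it.

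**Conclusion.** The contradiction is real for neutrophil recovery, real but narrower for lymphopenia, and no more than an unclear Day 1 action for the pre-cycle counts. It should be corrected because it concerns holding and restarting a drug for which section 8.1.10 lists decreased blood counts among the common events. The practical reach is the 6 expansion patients and anyone still on treatment. The neutrophil conclusion takes the screening count as the entry baseline.

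A reader might infer more, in three ways that the documents do not support:

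- **That every patient with an ANC of 1.0 to 1.5 or platelets of 75 to 100 is caught.** The direct neutrophil contradiction needs a prior Grade 3–4 event, and the platelet restart grades agree.
- **That it is likely to arise among the patients at the MTD.** Section 8.1.10 gives decreased neutrophils in 20.9%, platelets in 21.3% and lymphocytes in 28.1%, without a breakdown by grade. With no Grade 3–4 rates, the frequency cannot be estimated.
- **That it undermines the MTD or the endpoints.** Section 6.4 treats the MTD as determined, and no further DLT-driven decision is described for the expansion patients. Grade 4 neutropenia is a DLT whatever restart count is used. Sections 2.2.1 and 6.5.1 define the safety endpoint by the number, frequency and severity of adverse events, not by delays or exposure. No effect on the 8-week ORR rule is shown.

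**What to change.** Reconcile section 4.3.1, the section 4.5.1 paragraphs and Table 4.5 so that each cell line has one restart rule and one start-of-cycle rule. The revised text should also state:

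- whether the baseline exception covers lymphopenia;
- what happens on Day 1 if the pre-cycle counts are not met;
- whether the differing inequality at an ANC of exactly 1.0 is intended;
- which text governs if any difference remains.

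This review takes no position on which counts are right; that is for the sponsor's clinicians. The cost is an amendment to protocol wording, with no change to sample size, visits or analysis.

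### Table 4.5 does not give one outcome when a veliparib toxicity returns at a different grade; in the main case the choice is same dose or discontinue

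*Combined protocol and SAP*

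**What the plan says.** Section 4.5.1 makes the table the operative rule: "The dose of veliparib will be managed according to Table 4.5 below, and the dose levels in Table 4.3". Its lead-in adds that, for Grade 3 or 4 toxicity, "the veliparib dose will be held until the toxicity resolves to Grade 1 or lower" (or to baseline, if Grade 2 was present at entry). It says nothing about a second episode at another grade.

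For non-hematologic events attributed to veliparib, the Grade 2 and Grade 3 rows both begin with an interruption and then "Re-initiate veliparib at the same dose". Both continue: "If the same toxicity recurs at Grade 2, interrupt until recovery to ≤ Grade 1. Re-initiate veliparib at the next lower dose level". The Grade 3 row alone adds: "If toxicity recurs at Grade 3, discontinue veliparib". The Grade 4 row reads: "Discontinue veliparib and treat with appropriate medical therapy".

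The blood-count rows follow a similar pattern. The Grade 4 neutrophil row says "Re-initiate veliparib at the same dose level. If toxicity recurs at Grade 4: temporary dose interruption until recovery to" a stated count, followed by a reduction to the next lower level. The Grade 4 platelet and lymphocyte rows restart a first event at the next lower level and then say: "If toxicity recurs at grade 4: discontinue veliparib".

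**The concern.** A second episode at a new grade is both the first event at that grade and a recurrence of the toxicity. Where a row gives different actions for those two descriptions, a reader can reach either one from the same line of the table.

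In addition, a plain look-up by row puts some actions out of order. A non-hematologic Grade 2 event that returns at Grade 2 is reduced, but one that returns at Grade 3 goes back at the same dose. Grade 3 neutropenia that returns at Grade 3 is reduced, but if it returns at Grade 4, which section 4.3.1 lists as a DLT, it goes back at the same dose.

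What is at stake is whether two investigators with the same patient would give the same veliparib dose, or continue veliparib at all. That is a matter of patient safety and of consistent conduct.

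**Working it through.** The plan states no figure here, so the check is an enumeration of Table 4.5.

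**Inputs (section 4.5.1, Table 4.5).** *Same* means restart at the dose in use before the event. *Lower* means the next lower dose level.

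| Entry | Grade row | First event | Recurrence clause in that row |
|---|---|---|---|
| Non-hematologic | 2 | same | at 2: lower |
| Non-hematologic | 3 | same | at 2: lower; at 3: discontinue |
| Non-hematologic | 4 | discontinue | none |
| Neutrophils | 3 | same | at 3: lower |
| Neutrophils | 4 | same | at 4: lower |
| Platelets | 2 | same | at 2: lower |
| Platelets | 3 | lower | at 3: lower |
| Platelets | 4 | lower | at 4: discontinue |
| Lymphocytes | 3 | lower | at 3: lower |
| Lymphocytes | 4 | lower | at 4: discontinue |
| Anemia | 3 | same | none |
| Anemia | 4 | discontinue | none |

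Grade 2 neutropenia, lymphopenia and anemia need no adjustment, so they start no sequence.

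**Step 1: sequences.** I count ordered pairs of different grades in which the first event allows a restart and the second calls for an action:

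- Non-hematologic: 4 (2 to 3, 2 to 4, 3 to 2, 3 to 4)
- Neutrophils: 2 (3 to 4, 4 to 3)
- Platelets: 6 (all ordered pairs of 2, 3 and 4)
- Lymphocytes: 2 (3 to 4, 4 to 3)
- Anemia: 1 (3 to 4)

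The total is 4 + 2 + 6 + 2 + 1 = 15.

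**Step 2: two readings.** Reading A treats the second episode as the first event in its new row. Reading B applies that row's recurrence clause. The readings differ in eight sequences:

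| Sequence | Reading A | Reading B |
|---|---|---|
| Non-hematologic 2 to 3 | same | discontinue |
| Neutrophils 3 to 4 | same | lower |
| Neutrophils 4 to 3 | same | lower |
| Platelets 2 to 4 | lower | discontinue |
| Platelets 3 to 4 | lower | discontinue |
| Platelets 3 to 2 | same | lower |
| Platelets 4 to 2 | same | lower |
| Lymphocytes 3 to 4 | lower | discontinue |

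The other 15 − 8 = 7 have one outcome:

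- Non-hematologic 2 to 4 and 3 to 4, and anemia 3 to 4: discontinue.
- Non-hematologic 3 to 2: lower, written out in the Grade 3 row.
- Platelets 2 to 3 and 4 to 3, and lymphocytes 4 to 3: lower under both readings.

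**Step 3: ordering.** For the nine upward sequences, I compare reading A with the action for a recurrence at the original grade.

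- Non-hematologic 2 to 3: same, against lower for 2 to 2. Milder.
- Neutrophils 3 to 4: same, against lower for 3 to 3. Milder.
- Platelets 2 to 3, 2 to 4 and 3 to 4, and lymphocytes 3 to 4: lower, against lower. Equal.
- Non-hematologic 2 to 4 and 3 to 4: discontinue, so not milder.
- Anemia 3 to 4: discontinue, with no same-grade clause to compare.

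The inversion therefore appears in 2 of 9.

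**Step 4: is it settled elsewhere?** Sections 4.4 and 4.5.1 (lead-in) give no rule. Table 4.6, for nivolumab, does send a worsening Grade 2 toxicity to the higher-grade rows. Table 4.5 has no such link.

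**The case against.** The best reply is that each recurrence clause sits inside a grade row, after that row's first-event action, and so presupposes an earlier event of that grade. On that view *recurs at Grade 3* means a second Grade 3 event, and the table has a gap rather than two conflicting instructions. This is a fair reading, and part of it stands: nowhere does the table expressly order two different actions for one defined event. It does not close the point, for two reasons. The non-hematologic Grade 3 row uses *recurs* for a return at Grade 2 after a first event at Grade 3, so in this table the word can span grades. And if the same-grade reading is adopted throughout, reading A governs and both inversions in step 3 follow directly.

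A second reply is that section 4.5.1 calls these guidelines, the column is headed as recommendations, and section 4.7 lets the investigator stop treatment for any reason. That softens the consequence. It does not say which restart dose the table intends, and section 11.6 asks for conduct exactly as described, apart from emergencies.

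A reader might also take the adverse event rates in section 8.1.10 as the size of the problem. They are not. They are not split by grade, they do not count second episodes, and nausea, the most frequent, has its own management entry in Table 4.5.

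**Conclusion.** The point holds as an ambiguity in Table 4.5 that should be corrected. Eight of 15 grade-changing sequences have two outcomes. The main one is non-hematologic Grade 2 then Grade 3, where the readings are same dose and discontinuation. The other seven are one step apart: same or next lower dose for neutrophils 3 to 4 and 4 to 3 and for platelets 3 to 2 and 4 to 2; next lower dose or discontinuation for platelets 2 to 4 and 3 to 4 and for lymphocytes 3 to 4.

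Two stronger conclusions might be inferred, and the documents do not support them. One is that the whole table offers a choice between full dose and discontinuation, or treats worse recurrences more mildly. The first is true of one sequence and the second of two, and neutropenia never leads to discontinuation. The other is that the response rate is distorted. It is read at the first imaging (8 weeks) in 10 patients, and a patient would have to have an event, recover, restart and have a second event at another grade before that scan. The documents give no frequency for this, so no effect can be claimed.

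The result assumes no reduction before the first event and attribution of both episodes to veliparib. It takes no view on which action is right.

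**What to change.** Reconcile the rows of Table 4.5. State whether *recurs* means an earlier event of the same grade or any earlier episode of that toxicity, and check that each of the eight sequences above then has one stated outcome. The non-hematologic Grade 3 row, which already spells out a return at Grade 2, shows a workable format. Ask the clinical team to confirm whether the ordering in the non-hematologic 2 to 3 and neutropenia 3 to 4 sequences is intended. The choice of action in every sequence is theirs.

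The cost is wording in one table at the next amendment. No new data or patients are needed.
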